### **1.4.3 Discussion**

Due to the lack of mechanism- or compound-related safety signals and the antagonistic mode of action of Spesolimab (BI 655130) it is considered likely that PPP patients will not be exposed to undue risks and adverse events in relation to the information that is expected to be gained from this trial. Considering the medical need of the development of an effective and well tolerated drug specifically and directly treating PPP, the benefit of this trial is considered to outweigh the potential risks and justifies the administration of Spesolimab (BI 655130) to patients with PPP. The benefit-risk profile is thus considered appropriate for an experimental therapy at this stage of clinical development.

## 2. TRIAL OBJECTIVES AND ENDPOINTS

### 2.1 MAIN OBJECTIVES, PRIMARY AND SECONDARY ENDPOINTS

#### 2.1.1 Main objectives

To evaluate the long-term safety and efficacy of Spesolimab (BI 655130) in patients with PPP, who have completed previous Spesolimab (BI 655130) trials and are qualified for entry in this trial.

#### 2.1.2 Primary endpoint(s)

The primary endpoint is the occurrence of treatment emergent adverse events (TEAEs) up to week 260 of maintenance treatment.

Note: TEAEs are defined as all adverse events occurring between start of treatment in the extension trial and the end of its residual effect period. Adverse events that start before first drug intake in the extension trial and deteriorate under treatment during the extension trial will also be considered as 'treatment-emergent'.

#### 2.1.3 Secondary endpoint(s)

The following secondary endpoints are defined as described below. Note that for the secondary endpoints, any data collected after use of any rescue therapy or after 6 weeks following discontinuation of treatment (to allow for incorporation of the continuing maximum treatment effect period) in current trial are censored for the purpose of the primary estimand.

- Percent change in PPP ASI from baseline in parent trial at week 48, 96, 144, 192, 240 and 260
- Proportion of patients with PPP ASI50 compared to baseline in parent trial at week 48, 96, 144, 192, 240 and 260
- Proportion of patients with PPP PGA of 0 (clear) or 1 (almost clear) at week 48, 96, 144, 192, 240 and 260

### 3. DESCRIPTION OF DESIGN AND TRIAL POPULATION

#### 3.1 OVERALL TRIAL DESIGN

This open label, single-arm, multi-regimen, 5-year extension study investigates the long-term safety and efficacy of Spesolimab (BI 655130) in patients with PPP who have completed their treatment in previous Spesolimab (BI 655130) trials ('the parent/preceding/previous trial'). BI trial 1368-0016 is the first trial from which patients will roll over into this extension trial. At a later stage further patients may roll over from planned Phase III trials with Spesolimab (BI 655130).

Approximately 500 patients from the parent trials are expected to meet the entry criteria and are planned to be rolled over into this open-label extension study. Enrollment period will not be expanded in case less than 500 patients can roll over. Patients rolling over into 1368-0024 trial must have completed the treatment period as required in the parent trial. Ideally, the EoT visit of the preceding trial is the Screening visit (V1) of the extension trial. Procedures performed at the last visit of the preceding trial should not be repeated in 1368-0024 (see [Section 6.2.1](#) for details).

If patients lose their benefit during the course of the extension trial in their personal opinion or in the opinion of the investigator, or a preferred treatment option becomes available patients can discontinue trial participation after a discussion with the investigator. As in any other clinical trial patients can also revoke their consent at any time without the need to justify the decision. For all details please see [Section 3.3.4](#).

The extension study consists of a screening period lasting up to 28 days for patients rolling over from parent trials, followed by a 260 weeks treatment period and a 16 weeks safety follow-up period. 1st IMP administration in the extension trial should be done 28 days ( $\pm 7$  days visit window) after last IMP administration in preceding trial. The time window between last IMP administration in the parent trial and the first IMP administration in the extension trial may be extended in exceptional cases at the discretion of the Clinical Trial Leader on a case by case basis. Patients will receive open label Spesolimab (BI 655130) 600mg every 4 weeks subcutaneously during the treatment period. This is the highest maintenance dose from the first preceding trial 1368-0016 as this is assumed to provide the optimal treatment effect. At the same time the dose is safe and well tolerated based on the available data so far (see [Figure 3.1: 1](#)).

## Trial Design

[figure not shown]

Figure 3.1: 1 One single arm: Spesolimab (BI 655130) 600mg s.c. q4w over 260 weeks

For patients who terminate study drug prematurely in this extension study the subsequent visit will be replaced by an early EoT visit followed by an EoS visit 16 weeks after the last study drug administration (see Figure 3.1: 1).

Interim analyses of [REDACTED] and clinical data may be performed throughout the conduct phase of this 5-year study to support future trial applications, investigator brochures, regulatory documents and scientific publications. The final analysis of the entire trial data will be performed once all patients have completed the last scheduled trial visit. Individual patient participation is concluded when the patient has completed the last scheduled visit. The end of whole study is defined as “last patient out”; i.e. last scheduled visit completed by the last patient in the study.

An independent Data Monitoring Committee will evaluate safety and efficacy data on a continuous basis.

### 3.2 DISCUSSION OF TRIAL DESIGN, INCLUDING THE CHOICE OF CONTROL GROUP(S)

This open label extension study aims to offer active long-term treatment to patients having benefited from treatment with Spesolimab (BI 655130) in the previous Spesolimab (BI 655130) trials, and to characterize the safety of Spesolimab (BI 655130) long-term treatment. It will also characterize the clinical outcome over a long period of Spesolimab (BI 655130) treatment. Spesolimab (BI 655130) as s.c. treatment is to be offered to maintain the clinical response in PPP that was reached in the parent trials. A control group is not planned in this extension study because there is no established standard of care for PPP and active treatment should be offered for this high unmet needs patient population.

It is acknowledged that the reporting of data for this open-label trial will likely be biased due to, among others, selection and reporting bias. This is, however, deemed acceptable given that all patients who respond to previous treatment and who continue into this extension trial will be able to receive an active treatment with Spesolimab (BI 655130) for their ongoing disease.

### 3.3 SELECTION OF TRIAL POPULATION

Patients in this long-term open label extension trial will be rolled-over from previous trials with BI 651330. Patients must have completed the treatment of the previous trial and must meet the eligibility criteria for this open label extension trial. Patients must be willing and eligible to continue a long-term treatment with Spesolimab (BI 655130) for up to 5 years.

A log of all patients enrolled into the trial (i.e. who have signed informed consent) will be maintained in the Investigator Site File (ISF) irrespective of whether they have been treated with investigational drug or not.

If a patient is enrolled in error (does not meet all inclusion criteria or meets one or more exclusion criteria on the day of enrolment), the sponsor should be contacted immediately.

#### 3.3.1 Main diagnosis for trial entry

Patients with PPP who have completed and clinically responded to the treatment with study drug (Spesolimab) in previous trials with Spesolimab (BI 655130).

Please refer to [Section 8.3.1](#) (Source Documents) for the documentation requirements pertaining to the in- and exclusion criteria.

#### 3.3.2 Inclusion criteria

Each patient must meet all of the following inclusion criteria to be included into the trial:

1. Signed and dated written informed consent for the current trial 1368-0024, in accordance with ICH-GCP and local legislation prior to admission to the current trial
2. Male or female patients who have completed the treatment period in one of the parent trials without premature discontinuation
3. Patients who have obtained an individual health benefit, per investigator judgement (**e.g.** PPP PGA of 0 (clear) or 1 (almost clear) or other clinical improvement), from treatment in the parent trial.
4. Women of childbearing potential must be ready and able to use highly effective methods of birth control per ICH M3 (R2) that result in a low failure rate of less than 1% per year when used consistently and correctly. A list of contraception methods meeting these criteria is provided in [Section 4.2.3](#) and in the patient information. *Note: A woman is considered of childbearing potential, i.e. fertile, following menarche and until becoming postmenopausal unless permanently sterile. Permanent sterilisation methods include hysterectomy, bilateral salpingectomy and bilateral oophorectomy. Tubal ligation is not a method of permanent sterilization. A postmenopausal state is defined as no menses for 12 months without an alternative medical cause.*

### 3.3.3 Exclusion criteria

Patients meeting any of these exclusion criteria must not be enrolled into the trial:

1. Women who are pregnant, nursing, or who plan to become pregnant while in the trial.
2. Patients who experienced study treatment-limiting adverse events during the parent trial.
3. Severe, progressive, or uncontrolled condition such as renal, hepatic, haematological, endocrine, pulmonary, cardiac, neurologic, cerebral, or psychiatric disease, or signs and symptoms thereof.
4. Patients with congestive heart disease, as assessed by the investigator.
5. Patient with a transplanted organ (with exception of a corneal transplant >12 weeks prior to screening in parent trial) or who have ever received stem cell therapy (e.g., Prochymal).
6. Known history of lymphoproliferative disease, including lymphoma, or signs and symptoms suggestive of possible lymphoproliferative disease (e.g. splenomegaly).
7. Any documented active or suspected malignancy or history of malignancy within 5 years prior to screening in parent trial, except appropriately treated basal cell carcinoma of the skin, squamous cell carcinoma of the skin or in situ carcinoma of uterine cervix.
8. Patients who have developed active or severe infective disease and opportunistic infections/infective diseases.
  - Patients with **latent** TB during preceding trial are allowed to be included in study 1368-0024, provided they have received and/or receive currently appropriate treatment according to local guidelines. See [Section 5.2.3](#) for more details.
9. Use of any restricted medication as specified in [Section 4.2.1](#) or any drug considered by the investigator likely to interfere with the safe conduct of the study since the last visit of the previous Spesolimab (BI 655130) trial and during screening period for the current trial.
10. Plans for administration of live vaccines during the study period or since parent trial.
11. History of allergy/hypersensitivity to the systemically administered trial medication agent or its excipients.
12. Major surgery (major according to the investigator's assessment) performed since the last visit of previous Spesolimab (BI 655130) trial or planned during the current trial (e.g. hip replacement, aneurysm removal, stomach ligation), as assessed by the investigator.
13. Patient has received surgical treatment of focal infection (e.g. tonsillectomy or dental therapy) since the last visit of previous Spesolimab (BI 655130) trial or planned during the current trial.
14. Total white blood count (WBC) <3,000/ $\mu$ L (SI unit <3.00 GI/L), or platelets <100,000/ $\mu$ L (SI unit <100 GI/L) or neutrophils <1,500/ $\mu$ L (SI unit <1.5 GI/L), or hemoglobin <8.5 g/dL (SI unit <85 g/L) at screening.
15. Aspartate aminotransferase (AST) or alanine aminotransferase (ALT) >2x the upper limit of normal, or total bilirubin >1.5x the upper limit of normal (patients with Gilbert's syndrome are not excluded) at screening.
16. Any condition which in the opinion of the investigator affects the safety of the patients, the patients' ability to participate in this trial or could compromise the quality of data.
17. Previous participation in this trial.
18. Presence of acute demyelinating neuropathy

### 3.3.4 Withdrawal of patients from the trial

Patients may discontinue the trial or withdraw consent to trial participation as a whole (“withdrawal of consent”) with very different implications; please see [Sections 3.3.4.1](#) and [3.3.4.2](#) below.

The decision to discontinue the trial or withdraw consent to trial participation and the reason (if known) must be documented in the patient files and CRF. If applicable, consider the requirements for Adverse Event collection reporting (please see [Section 5.2.6](#))

Patients withdrawn from the trial, independent of the underlying reason, should complete an early EoT-visit and the 16 week FUP period for safety reasons (please see [Flow Chart](#) and [Section 6.2.3.1](#)). This should also be proposed to patients who withdraw their informed consent.

#### 3.3.4.1 Wish to discontinue trial treatment, non-compliance of patient, medical reason and intake of restricted medication

An individual patient will be withdrawn from the trial if:

- The patient wants to discontinue trial treatment, without the need to justify the decision. This includes patients losing individual perceived health benefit or becoming aware of a preferred treatment option.
- The patient has repeatedly shown to be non-compliant with important trial procedures and, in the opinion of both, the investigator and sponsor representative, is not willing or able to adhere to the trial requirements in the future.
- The patient can no longer receive trial treatment for medical reasons (such as surgery, adverse events – see also [Section 3.3.4.3](#), other diseases, or pregnancy). The patient took restricted medication which is not allowed acc. to [Section 4.2.1](#) and [Table 4.2.1: 1](#).

#### 3.3.4.2 Implications due to loss of treatment response

- Patients who need to take rescue medication must be discontinued from the trial. Rescue therapy is defined as the use of topical corticosteroids or other topical treatment, systemic immunomodulating treatments or biologics and therapy such as tonsillectomy, for the treatment of worsening of PPP. For the complete list and all details of restricted medication see [Section 4.2.1](#) and [Table 4.2.1: 1](#).
- The following additional trial treatment discontinuation criteria apply from Visit 2 onwards:
  - Increase of pustulation severity compared to baseline (baseline (V1) of extension trial)AND
  - Loss of PPP ASI by  $\geq 5$  points compared to baseline (baseline (V1) of extension trial)

A patient who meets the trial treatment discontinuation criteria at 2 consecutive visits must be discontinued from the trial treatment and administered standard of care therapy.

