After a patient's EoS-visit in the extension trial the investigator does not need to actively monitor the patient for new AEs but should only report new malignancies or the exacerbation of existing malignancies, trial treatment related SAEs and trial treatment related AESIs of which the investigator may become aware of by any means of communication. See [Section 5.2.6.2.2](#) for details.

 Please see [Section 5.2.6.2.1](#) for important instructions regarding AE collection in parent and extension trial.

Repeat every 16 weeks, at EoT and EoS

Current smoking status needs to be completely re-assessed at V1 of extension trial. Afterwards changes in smoking should be evaluated approximately once per year at visits in Wk 48, 96, 144, 192, 240, EoT and EoS;

[REDACTED]

[REDACTED]

[figure not shown]
[figure not shown]

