## 5. ASSESSMENTS

### 5.1 ASSESSMENT OF EFFICACY

#### 5.1.1 Palmoplantar Pustulosis Area and Severity Index (PPP ASI)

The Palmoplantar Pustulosis Area and Severity Index (PPP ASI) is an investigator assessment of the extent and severity of pustular and plaque lesions on the palms and soles presenting in PPP patients. The adaptation from PASI, an established measure of severity and area of psoriatic lesions in patients with psoriasis, by Bhushan et.al [R16-5334] will be used in this trial.

This tool provides a numeric scoring for patients overall PPP disease state, ranging from 0 to 72. It is a linear combination of the percent of surface area of skin that is affected on the palms and soles of the body and the severity of erythema, pustules, and scaling (desquamation).

The PPP ASI will be measured at the timepoints noted in the [Flow Chart](#). The PPP ASI is provided in [Appendix 10.1.1](#).

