#### **The following assessments are done at every visit (every 4 weeks) during treatment period (V2 – EoT inclusively):**

##### Vital signs, plus EoS

Measurement of vital signs should precede blood sampling and will be assessed pre-dose at all dosing visits and at approx. 10 minutes after study drug administration.

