##### Pregnancy test, plus EoS

Urine pregnancy testing for all women of child-bearing potential will be conducted on-site every 4 weeks and must be negative to continue treatment. More frequent testing should be done if required by the local regulation and / or authority or per investigator judgment. The urine pregnancy testing should be done **prior to** study drug administration. Study drug should only be administered in case of a negative test result. In case of a positive urine test result, the visit will be re-scheduled, IMP administration postponed and serum pregnancy test performed. In case of a positive serum test, the patient must be discontinued from the trial. In case of a negative serum test the Sponsor trial team should be contacted to discuss if the previous visit can still be re-scheduled or must be skipped.

See also [Flow Chart](#).

Concomitant therapy, plus EoS

Data concerning concomitant medications and procedures will be collected throughout the trial. These data will be obtained at scheduled or unscheduled trial visits based on information provided spontaneously by the patient or as a result of questioning the patient.

Adverse Event review/discussion, plus EoS

To be done at every visit, see [Section 5.2.6](#) for more details;

IRT Contact

IRT system to be contacted at each visit until EoT (incl.), see [Flow Chart](#);

IMP administration

IMP is administered at each visit from V2 to EoT (incl.), see Flow Chart;

Local tolerability, plus EoS

Local tolerability at the administration site of the subcutaneous injection will be assessed during the study drug administration on site and retrospectively by asking the patient if local tolerability related AEs occurred. Any observed local tolerability reaction, e.g. “swelling”, “induration”, “heat”, “redness”, “pain”, and other findings should be reported as an adverse event.

**The following assessments are done every 16 weeks during treatment period (EoT inclusively), 1st assessment after screening at week 16 (V6):**

Physical examination, plus EoS

See Flow Chart and [Section 5.2.1](#) for details;

Safety laboratory tests, plus EoS

(except: TSH and HbA1c only to be done once per year)

See Flow Chart and [Section 5.2.3](#) for details;

PPP PGA, [REDACTED], plus EoS

See Flow Chart and [Section 5.1.2](#) for details;

PPP ASI [REDACTED], plus EoS

See Flow Chart and [Sections 5.1.1](#) and [5.1.5](#) for details;

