## 10. APPENDICES

### 10.1 INSTRUCTIONS FOR USE

#### 10.1.1 Palmoplantar Pustulosis Area and Severity Index (PPP ASI)

Score	0	1	2	3	4	5	6
Erythema (E)	None	Slight	Moderate	Severe	Very severe		
Pustules (P) (total)	None	Slight	Moderate	Severe	Very severe		
Desquamation (D) (scaling)	None	Slight	Moderate	Severe	Very severe		
Area affected (%)*	0	<10	10<30	30<50	50<70	70<90	90 - 100

\* where area assessed is glabrous skin on the palms/ soles

PPP ASI = [(E+P+D) Area x 0.2 (right palm)] + [(E+P+D) Area x 0.2 (left palm)] + [(E+P+D) Area x 0.3 (right sole)] + [(E+P+D) Area x 0.3 (left sole)]

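### The mandatory worsening stop in Protocol 3.3.4.2 asks for a fall in PPP ASI, which is an improvement; its two-visit confirmation also needs a stated interval (minor)

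*Protocol*

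**What the plan says.** Protocol 3.3.4.2, on loss of treatment response, adds a stopping rule that applies from Visit 2. It has two criteria joined by AND, both measured against V1 of the extension trial. Pustulation must be more severe, and there must be a "Loss of PPP ASI by" at least 5 points. The consequence is compulsory: "A patient who meets the trial treatment discontinuation criteria at 2 consecutive visits must be discontinued from the trial treatment".

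The scale is described in Protocol 5.1.1: "This tool provides a numeric scoring for patients overall PPP disease state, ranging from 0 to 72". Appendix 10.1.1 scores erythema (E), pustules (P) and desquamation (D) from 0 (none) to 4 (very severe) and area from 0 to 6, and combines them as "PPP ASI = [(E+P+D) Area x 0.2 (right palm)] + [(E+P+D) Area x 0.2 (left palm"), with each sole added at weight 0.3.

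Protocol 6.2.2 gives two frequencies. Vital signs, adverse event review and dosing fall under "The following assessments are done at every visit (every 4 weeks) during treatment period". PPP ASI and PPP PGA fall under "The following assessments are done every 16 weeks during treatment period", starting at week 16. Flow Chart footnote 19 agrees for the later visits: "Repeat every 16 weeks, at EoT and EoS".

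**The concern.** The main problem is direction. Every component of PPP ASI increases with disease, so a loss of points is a better score. The pustulation criterion is written as worsening, and the PPP ASI criterion joined to it is written as improvement. A rule meant to take non-benefiting patients off treatment would, as worded, select some improving patients and pass over relapsing ones.

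The second problem is one of definition. Visits are 4-weekly and PPP scoring is 16-weekly, and the rule does not say which sequence its two consecutive visits belong to. Protocol Table 4.2.1: 1 does specify the visits at which PPP is assessed when it means those; the stopping rule has no such qualifier.

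At stake is whether a compulsory rule in a five-year multi-centre trial can be applied and audited as written. The Amendment 3 rationale (Protocol 11.3) says the stop was made compulsory so that patients who no longer benefit leave the trial.

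**Working it through.** **Inputs.** Score formula and item ranges: Protocol Appendix 10.1.1. Score range: Protocol 5.1.1. Visit and scoring intervals: Protocol 6.2.2, Flow Chart footnote 19, and SAP Table 6.7: 2 (M1 to M17). Dose of 600 mg every 4 weeks: Protocol 4.1.2. Drug is given after PPP scoring: Flow Chart footnote 15.

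**1. Reproduce the stated range.** Maximum = (4 + 4 + 4) × 6 × (0.2 + 0.2 + 0.3 + 0.3) = 12 × 6 × 1 = 72. The minimum is 0. This matches Protocol 5.1.1 and fixes the direction: higher is worse.

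**2. Who can meet the criterion.** Let change = later PPP ASI − V1 PPP ASI.
- Literal wording: change ≤ −5. The score cannot go below 0, so V1 PPP ASI must be at least 5.
- Intended wording: change ≥ +5. The score cannot exceed 72, so V1 PPP ASI can be anything up to 72 − 5 = 67.

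**3. Two examples.** Assume the same scores on both palms and both soles, so that PPP ASI = (E + P + D) × Area. Pustulation severity is taken as the P item, because 3.3.4.2 does not name the measure.

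| | V1 | Later | Change | Pustules | Literal rule | Intended rule |
|---|---|---|---|---|---|---|
| A | (1+1+1) × 1 = 3 | (2+3+2) × 3 = 21 | +18 | 1 to 3 | not met | met |
| B | (2+1+3) × 3 = 18 | (1+2+1) × 2 = 8 | −10 (10/18 = 56%) | 1 to 2 | met | not met |

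B shows that the literal combination is possible, so the wording defines a real but wrong group rather than an empty one.

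**4. Schedule.** Visit v (2 to 67) falls at week 4 × (v − 2). That gives 66 dosing visits and 65 pairs of adjacent visits. Scheduled on-treatment scores fall at weeks 16, 32, …, 256 (16 of them) and week 260, 17 in all.
- Adjacent 4-weekly visits with a score scheduled at both: 1 of 65 (V66/V67, weeks 256 and 260). The earliest trigger is week 260, so at most the final dose could be withheld.
- Adjacent scored visits: 17 − 1 = 16 pairs, of which 15 are 16 weeks apart and 1 is 4 weeks apart. The earliest trigger is week 32.
- If an investigator adds a score at V7 after a positive week 16 score, either reading triggers at week 20.

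**5. Cost of waiting for a scheduled confirmation.** From a positive score at week 16 to confirmation at week 32, doses are given at weeks 16, 20, 24 and 28: 4 × 600 mg = 2,400 mg.

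**The case against.** The best reply is that nobody would misread the rule. The section concerns loss of response, the companion criterion is worsening, the consequence is a move to standard care, and the amendment rationale speaks of lost benefit. In that setting the phrase is shorthand for losing PPP ASI response. This stands as evidence of intent, and nothing in the documents shows a site applying the rule the wrong way round. It does not correct an operative sentence that says the opposite.

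On the schedule, a PPP ASI criterion can be met only where PPP ASI is scored. The SAP's efficacy visits (Table 6.7: 2) and its neighbouring-visit imputation rule (6.6.2) support reading visits as scored visits, and on that reading the rule already works from week 32. This largely stands. A reader might infer from the count of 1 pair in 65 that the stop cannot operate before week 260, but that follows from one reading only. The interval is an ambiguity, not an error.

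A reader might also infer that the patients excluded by the literal wording are those named in inclusion criterion 3, "Patients who have obtained an individual health benefit, per investigator judgement", whose example is a PPP PGA of 0 or 1. The documents do not support that. PPP PGA ignores area. All three components at 1 give a PGA of 1; if the PPP ASI severities are also 1 (an assumption, since the scales are separate), PPP ASI = 3 × area score, which is 6 at area score 2 and 18 at area score 6. A PGA of 0 would give 0 on the same assumption, but the criterion also accepts other clinical improvement. No distribution of V1 PPP ASI is given, so the share below 5 is unknown.

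Finally, other routes cover much of the risk. Rescue or restricted medication forces discontinuation (3.3.4.1, 3.3.4.2, Table 4.2.1: 1), and patients can leave for lost benefit in their own or the investigator's opinion (3.1). Worsening of PPP is recorded as an adverse event (5.2.6.1.1), adverse events are reviewed every 4 weeks, and unscheduled visits may add assessments (6.2.2). This stands and keeps the point minor.

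**Conclusion.** The PPP ASI criterion is wrong as written, and the error is minor. Its literal meaning is improvement of 5 points or more; it conflicts with the criterion it is joined to, and it is out of reach for any V1 score below 5. This rests only on the formula and range in the protocol. The examples also assume equal scores at all four sites and the P item as the pustulation measure.

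The confirmation interval is a secondary clarification: the two readings place the earliest stop on scheduled data at week 32 or week 260.

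Stopping dates feed the 6-week censoring of the secondary endpoints and the responder denominators, so a reader might infer bias in those summaries. Nothing in the documents lets that be sized, the analyses are descriptive, and no such effect is claimed.

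**What to change.** In Protocol 3.3.4.2, replace the second criterion with *increase in PPP ASI of at least 5 points compared to V1 of the extension trial*. Keep the AND join and the start at Visit 2.

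Replace the trigger with *at 2 consecutive PPP assessments at least 4 weeks apart (scheduled or unscheduled)*, and have the sponsor confirm the intended interval. A minimum interval is needed because otherwise two scores a few days apart would force a stop. The sponsor should also say whether 4 weeks is counted in nominal visits or in days: with ±7-day windows, adjacent 4-weekly visits can fall 28 − 14 = 14 days apart.

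The cost is two phrases in the next amendment and a clarification letter to sites. The analysis is unchanged, since SAP 6.7 already assigns unscheduled efficacy measurements to time windows. The downside is that, except for the week 256/260 pair, confirmation on scheduled scores alone takes 16 weeks and the four doses shown above. If the sponsor wants confirmation at the next 4-weekly visit, the protocol must require an added PPP assessment there after a first positive score, which would bring the earliest stop to week 20.
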